10.5 APPENDIX 5: GENETICS

Not applicable.

10.6 APPENDIX 6: LIVER SAFETY: SUGGESTED ACTIONS AND FOLLOW-UP ASSESSMENTS

Not applicable.

10.7 APPENDIX 7: MEDICAL DEVICE INCIDENTS: DEFINITION AND PROCEDURES FOR RECORDING, EVALUATING, FOLLOW-UP, AND REPORTING

Not applicable.

10.8 APPENDIX 8: COUNTRY-SPECIFIC REQUIREMENTS

Not applicable.

10.9 APPENDIX 9: DESENSITIZATION RESPONSE CRITERIA

The target cPRA (ie, reduction of cPRA required to achieve at least 100% increase of likelihood of compatible donor [LCD]) is calculated according to the following equation (22). Examples of target cPRA reduction are presented in [Table 13](#).

$$LCD = 1 \text{ in } \frac{1}{1 - cPRA}$$

Table 13 - Examples of target cPRA reduction

Baseline		Target	
cPRA	LCD	cPRA	LCD
99.99%	1:10000	99.98%	1:5000
99.90%	1:1000	99.80%	1:500
99.80%	1:500	99.60%	1:250
99.60%	1:250	99.20%	1:125
99.50%	1:200	99.00%	1:100
99.00%	1:100	98.00%	1:50
97.50%	1:40	95.00%	1:20
95.00%	1:20	90.00%	1:10
90.00%	1:10	80.00%	1:5
80.00%	1:5	60.00%	1:2.5

Abbreviations: cPRA = calculated panel reactive antibodies, LCD = likelihood of compatible donor

Participants with baseline cPRA 100.00% will be assigned with cPRA 99.99% for computational purpose.

Antibody titer is defined as the last dilution of serum at which positive results is obtained (eg, MFI ≥ 2000) (54). Examples of antibody titer based on MFI are illustrated in Table 14.

Table 14 - Examples of antibody titer

	Neat Serum	1:2	1:4	1:8	1:16	1:32	Titer
Antigen 1 MFI	13430	12492	6250	3123	1550	790	8
Antigen 2 MFI	18320	20820	10501	5206	2604	1302	16
Antigen 3 MFI	11020	5493	2750	1384	688	360	4

Abbreviations: MFI = mean fluorescence intensity

Using similar concept, Table 16 illustrates an example in which the second predefined desensitization criterion (ie, $\geq 75\%$ reduction in antibody titer from baseline to achieve target cPRA, see Table 15) may be met. In this example, participant's baseline cPRA is measured by SAB as 97.50%, the target cPRA is therefore 95.00% as defined in Table 13. Through serial dilution of the serum collected at baseline, titer required to achieve target cPRA is 16 (ie, achieved at 1:16 dilution). Subsequent post-treatment serum is therefore diluted at 1:4 (ie, 75% reduction from 1:16) to determine whether target cPRA is achieved. At Cycle 3 Day 1, target cPRA is reached at 1:4 dilution therefore meeting the aforementioned predefined desensitization criterion.

Table 15 - 75% reduction in antibody titer from baseline

Baseline	75% Reduction			
	Titer	Dilution	Titer	Dilution
2	1:2	1	Neat	
4	1:4	1	Neat	
8	1:8	2	1:2	
16	1:16	4	1:4	
32	1:32	8	1:8	
64	1:64	16	1:16	
128	1:128	32	1:32	
256	1:256	64	1:64	
512	1:512	128	1:128	

Table 16 - Example of $\geq 75\%$ reduction in antibody titer from baseline to achieve target cPRA

	Neat Serum	1:2 Titer = 2	1:4 Titer = 4	1:8 Titer = 8	1:16 Titer = 16	Response Criterion Met
Baseline cPRA	97.50%	97.50%	97.50%	96.00%	95.00% (target cPRA)	
C2D1 cPRA	96.00%		96.00%			No
C3D1 cPRA	96.00%		95.00%			Yes

Abbreviations: C2D1 = Cycle 2 Day 1, C3D1 = Cycle 3 Day 1, cPRA = calculated panel reactive antibodies

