4.3 PRIMARY ENDPOINT(S) ANALYSIS

4.3.1 Definition of endpoint(s)

The primary endpoint in the Phase 1 portion of the study will focus on safety, ie, AEs/SAEs and laboratory abnormalities. Analysis details of these safety parameters are presented in [Section 4.7.2](#) and [Section 4.7.3.1](#).

In the Phase 2 portion of the study, the primary efficacy endpoint will be RR, to be defined as the proportion of participants meeting at least one of the predefined desensitization efficacy criteria, from baseline up to 26 weeks after treatment period, measured by SAB assay per central laboratory assessment as follows:

- Reduction in cPRA resulting in at least 100% increase of likelihood of finding a compatible donor for target cPRA
- Reduction in antibody titer ($\geq 75\%$ reduction from baseline) to achieve target cPRA
- Elimination of ≥ 1 anti-HLA-antibody (ie, MFI reduced to < 2000) as measured by a SAB assay, for antibodies with baseline MFI ≥ 3000

RR criterion 1: target cPRA

The target cPRA, defined as the reduction of cPRA required to achieve at least 100% increase of likelihood of compatible donor (LCD), is calculated according to the following equation:

$$LCD = 1 \text{ in } \frac{1}{1 - cPRA}$$

Participants with baseline cPRA 100.00% will be assigned with cPRA 99.99% for computational purpose. In addition, cPRA values will be rounded to 2 decimal places prior to LCD calculation ($\geq xx.xx5$ =round up, $< xx.xx5$ =round down).

RR criterion 2: antibody titer

Antibody titer is defined as the last dilution of serum at which positive results is obtained (eg, MFI ≥ 2000). To potentially meet the second RR criterion, serial dilution of the serum collected at baseline is performed until the target cPRA is achieved. If subsequent post-treatment serum is diluted at $\geq 75\%$ reduction from the baseline dilution that achieved target cPRA, and again meet target cPRA anytime within the 26-week post-treatment period, participant will have met RR criterion 2.

RR criterion 3: anti-HLA-antibody

An anti-HLA-antibody is considered to be eliminated if its MFI is reduced to < 2000 at post-treatment. Only antibodies with baseline MFI ≥ 3000 will be included for assessment under this criterion.

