4.3.2 Main analytical approach

The primary efficacy analysis is based on a treatment policy estimand introduced in [Section 1.2.1](#).

This primary estimand is defined according to the following attributes:

- The endpoint is RR, as defined in [Section 4.3.1](#).
- The treatment condition of interest is isatuximab
- The analysis population is the efficacy-evaluable population (defined in [Section 3](#))
- The study intervention interruption/discontinuation intercurrent event will be handled with the treatment policy strategy. RR will be assessed based on the 3 criteria irrespective of study intervention interruption/discontinuation.
- Population-level summary will be RR, defined as the proportion of participants meeting at least one of the predefined desensitization efficacy criteria (refer to [Section 4.3.1](#)), along with and two-sided 95% confidence intervals using the Clopper-Pearson method.

Proportion of participants meeting each criterion will also be tabulated.

Calculation details and examples on RR criteria 1 and 2 are provided in Appendix 4, [Section 5.4.2](#) (DESENSITIZATION response criteria).

For RR criterion 3, elimination of anti-HLA-antibody will be determined for each applicable molecular specificity.

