5.4.2 DESENSITIZATION response criteria

The target cPRA (ie, reduction of cPRA required to achieve at least 100% increase of LCD is calculated according to the following equation (2). Examples of target cPRA reduction are presented in [Table 8](#).

$$LCD = 1 \text{ in } \frac{1}{1 - cPRA}$$

Table 8 - Examples of target cPRA reduction

Baseline		Target	
cPRA	LCD	cPRA	LCD
99.99%	1:10000	99.98%	1:5000
99.90%	1:1000	99.80%	1:500
99.80%	1:500	99.60%	1:250
99.60%	1:250	99.20%	1:125
99.50%	1:200	99.00%	1:100
99.00%	1:100	98.00%	1:50
97.50%	1:40	95.00%	1:20
95.00%	1:20	90.00%	1:10
90.00%	1:10	80.00%	1:5
80.00%	1:5	60.00%	1:2.5

Abbreviations: cPRA = calculated panel reactive antibodies, LCD = likelihood of compatible donor

Participants with baseline cPRA 100.00% will be assigned with cPRA 99.99% for computational purpose.

Antibody titer is defined as the last dilution of serum at which positive results is obtained (eg, MFI ≥ 2000) (3). Examples of antibody titer based on MFI are illustrated in [Table 9](#).

Table 9 - Examples of antibody titer

Neat Serum	1:2	1:4	1:8	1:16	1:32	Titer
Antigen 1 MFI	13430	12492	6250	3123	1550	790
Antigen 2 MFI	18320	20820	10501	5206	2604	1302
Antigen 3 MFI	11020	5493	2750	1384	688	360

Abbreviations: MFI = mean fluorescence intensity

Using similar concept, [Table 11](#) illustrates an example in which the second predefined desensitization criterion (ie, $\geq 75\%$ reduction in antibody titer from baseline to achieve target cPRA, see [Table 10](#)) may be met. In this example, participant's baseline cPRA is measured by SAB as 97.50%, the target cPRA is therefore 95.00% as defined in [Table 8](#). Through serial dilution of the serum collected at baseline, titer required to achieve target cPRA is 16 (ie, achieved

at 1:16 dilution). Subsequent post-treatment serum is therefore diluted at 1:4 (ie, 75% reduction from 1:16) to determine whether target cPRA is achieved. At Cycle 3 Day 1, target cPRA is reached at 1:4 dilution therefore meeting the aforementioned predefined desensitization criterion.

Table 10 - 75% reduction in antibody titer from baseline

Baseline		75% Reduction	
Titer	Dilution	Titer	Dilution
2	1:2	1	Neat
4	1:4	1	Neat
8	1:8	2	1:2
16	1:16	4	1:4
32	1:32	8	1:8
64	1:64	16	1:16
128	1:128	32	1:32
256	1:256	64	1:64
512	1:512	128	1:128

Table 11 - Example of ≥75% reduction in antibody titer from baseline to achieve target cPRA

	Neat Serum	1:2 Titer = 2	1:4 Titer = 4	1:8 Titer = 8	1:16 Titer = 16	Response Criterion Met

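### The titer-2 row of the criterion 2 lookup table is labelled a 75% reduction but is 50%, which contradicts the ≥75% rule in SAP 4.3.1

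*Protocol*

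**What the plan says.** The primary efficacy endpoint is the "proportion of participants meeting at least one of the predefined desensitization efficacy criteria" (SAP Section 4.3.1). There are three criteria, and meeting any one makes a responder.

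- **Criterion 1:** "Reduction in cPRA resulting in at least 100% increase of likelihood of finding a compatible donor for target cPRA".
- **Criterion 2:** "Reduction in antibody titer ($\geq 75\%$ reduction from baseline) to achieve target cPRA". The baseline serum is diluted serially until target cPRA is reached. SAP Section 4.3.1 then sets the test after treatment: "If subsequent post-treatment serum is diluted at $\geq 75\%$ reduction from the baseline dilution that achieved target cPRA", and target cPRA is met again, the criterion is fulfilled.
- **Criterion 3:** elimination of at least one anti-HLA antibody with a baseline MFI of 3000 or more.

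Protocol Section 10.9 refers the reader of criterion 2 to "Table 15 - 75% reduction in antibody titer from baseline". SAP Section 5.4.2 repeats it as "Table 10 - 75% reduction in antibody titer from baseline". Both tables have nine rows, and both begin with baseline titer 2 (dilution 1:2) paired with titer 1 (neat serum). Neither has a footnote marking that row as a floor or an exception.

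SAP Section 4.3.2 sends the analyst to Section 5.4.2 for the calculation of criteria 1 and 2. It also commits to a breakdown by criterion: "Proportion of participants meeting each criterion will also be tabulated".

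**The concern.** A fall from titer 2 to titer 1 is a halving, yet the table presents it as a 75% reduction. For a participant whose baseline serum reaches target cPRA at 1:2, the documents give two answers. Under the text of SAP Section 4.3.1 no testable dilution is low enough, so criterion 2 cannot be met. Under the table the participant meets criterion 2 by reaching target cPRA in neat serum. Two programmers working from the same SAP could report different criterion 2 results.

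What is at stake is the separate criterion 2 proportion. Protocol Section 3.1 explains that antibody strength is judged by dilution rather than by quantifying MFI values. A line reported as a reduction of 75% or more should not include participants for whom only 50% was shown.

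**Working it through.** **Formula.** The documents' own example fixes it: "Subsequent post-treatment serum is therefore diluted at 1:4 (ie, 75% reduction from 1:16) to determine whether target cPRA is achieved". So reduction = 1 − (post-treatment titer ÷ baseline titer), and for the example 1 − 4/16 = 75%. The stated figure reproduces.

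**All nine rows of Protocol Table 15 (identical in SAP Table 10).**

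| Baseline titer | Listed post-treatment titer | Reduction | Titer needed for 75% |
|---|---|---|---|
| 2 | 1 (neat) | 50% | 0.5 |
| 4 | 1 (neat) | 75% | 1 |
| 8 | 2 | 75% | 2 |
| 16 | 4 | 75% | 4 |
| 32 | 8 | 75% | 8 |
| 64 | 16 | 75% | 16 |
| 128 | 32 | 75% | 32 |
| 256 | 64 | 75% | 64 |
| 512 | 128 | 75% | 128 |

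Eight rows are exact. Titer 2 fails: 0.25 × 2 = 0.5 lies below neat serum and cannot be reached by dilution. The lowest baseline titer at which a 75% reduction can be demonstrated is 4.

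**Effect on the composite.** In the titer-2 row, criterion 2 is tested in neat serum. Criterion 1 asks for the same target cPRA. I take it to be read in neat serum, as the worked example does: its measured baseline cPRA of 97.50% is the neat-serum value. Responder status is then:

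| Target cPRA in neat serum | Criterion 3 | Responder, row kept | Responder, row removed |
|---|---|---|---|
| No | No | No | No |
| No | Yes | Yes | Yes |
| Yes | No | Yes | Yes |
| Yes | Yes | Yes | Yes |

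The composite response rate changes by zero participants.

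**Effect on duration of response.** SAP Section 4.4.2.1 takes the earliest start and latest end across criteria. For these participants the criterion 2 interval comes from the same neat-serum results as the criterion 1 interval. Dropping it moves neither end.

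**Effect on the criterion 2 proportion.** Each participant credited through this row alone adds:

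- at the minimum of 12 per cohort (SAP Section 2): 1/12 = 8.3 percentage points;
- at 18 per cohort, assuming that the upper figure of 36 splits evenly over two cohorts: 1/18 = 5.6 percentage points.

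The documents do not give the number of participants with baseline titer 2. At zero, there is no effect.

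**Denominator.** SAP Section 5.4.1 computes percentages over participants with a non-missing observation. If titer-2 participants were set to missing for criterion 2, one who had not reached the target would leave the denominator only. As an illustration, 6/12 = 50.0% would become 6/11 = 54.5%, so a correction meant to be stricter would raise the figure.

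**The case against.** The strongest reply is that nothing important depends on this row. Responder status and duration of response are the same with or without it, and one descriptive line remains. That stands, and it sets the priority.

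A reader might infer that participants below the threshold are in fact credited and that the criterion 2 proportion is inflated. The documents do not support that, for three reasons.

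- The text of SAP Section 4.3.1, read literally, excludes the step from 1:2 to neat, and nothing says that the table overrides the text. The cross-references to the table from the criterion itself make its use plausible, not certain.
- Neat serum is the floor of the dilution series. Reaching target cPRA there shows a reduction of at least 50%, and the true reduction may be 75% or more. The 75% is undemonstrated; it has not been shown to be missed.
- There may be no participant with baseline titer 2.

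The reply does not remove the error in the table. The same row stands in both documents while the other rows are intact, so text extraction does not explain it. Protocol Table 15 and SAP Table 10 are also not titled as examples, unlike the neighbouring tables in the same sections.

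**Conclusion.** The point holds as an inconsistency between table and text. By the documents' own formula the titer-2 row is a 50% reduction under a 75% label, and 75% cannot be demonstrated from that baseline. If the table is applied over the text, the criterion 2 proportion could be overstated, within the per-participant range worked out above and by an unknown total that may be nil.

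A reader might also suspect that the primary response rate is overstated. It is not, provided criterion 1 is read in neat serum. The redacted null and alternative response rates play no part. This is a minor correction, worth making because it concerns the definition of a component of the primary endpoint and costs almost nothing.

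**What to change.** In Protocol Table 15 and SAP Table 10, remove the titer-2 row. Add one sentence to Protocol Section 10.9 and to SAP Sections 4.3.1 and 5.4.2: when the baseline serum reaches target cPRA at 1:2, criterion 2 cannot be demonstrated; the participant stays in the efficacy-evaluable denominator and counts as not meeting criterion 2; criterion 1 still applies. Stating the denominator closes the gap that the non-missing rule in SAP Section 5.4.1 would otherwise open.

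Keeping the row with a footnote that declares it a floor exception at 50% would also reconcile the documents, but the criterion 2 line could then no longer be described as a reduction of 75% or more throughout.

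The cost is one table row and a sentence in each document. No new data, assay work or change of sample size is needed. With the denominator fixed as above, the criterion 2 proportion stays the same or falls relative to applying the table as printed.

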10.10 APPENDIX 10: CLUSTER OF DIFFERENTIATION 38 BLOOD TEST INTERFERENCE GUIDELINE

Advancing Transfusion and
Cellular Therapies Worldwide

Association Bulletin #16-02

Date: January 15, 2016
To: AABB Members
From: [name], MT(ASCP)SBB—President
[name]—Chief Executive Officer
Re: Mitigating the Anti-CD38 Interference with Serologic Testing

Summary

A new class of therapeutic agents for multiple myeloma, CD38 monoclonal antibodies, can result in interference with blood bank serologic tests and thereby cause delays in issuing Red Blood Cell (RBC) units to patients receiving these agents. To minimize these delays, hospitals should set up procedures to inform the transfusion service when patients start receiving these agents. Considerations for the transfusion service, both before and after initiation of anti-CD38 therapy, are detailed below.

The AABB Clinical Transfusion Medicine Committee has developed this bulletin to provide background information and guidance to members regarding anti-CD38 interference with serologic testing. The bulletin includes recommendations for its prevention and treatment.

Association Bulletins, which are approved for distribution by the AABB Board of Directors, may include announcements of standards or requirements for accreditation, recommendations on emerging trends or best practices, and/or pertinent information. This bulletin contains information and recommendations. No new standards are proposed.

Background

CD38 monoclonal antibodies are a new treatment for multiple myeloma

CD38, an integral membrane protein that is highly expressed on myeloma cells, has been identified as an effective target antigen for monoclonal antibody therapies. In November 2015, the first therapeutic CD38 monoclonal antibody [daratumumab (Darzalex, Janssen Biotech, Horsham, PA)] was approved by the Food and Drug Administration.¹ Other CD38 monoclonal antibodies are under development.

CD38 monoclonal antibodies interfere with blood bank serologic tests

CD38 is weakly expressed on red cells. Anti-CD38 binds to CD38 on reagent RBCs, causing panreactivity in vitro.^{2,3} Plasma samples from anti-CD38-treated patients consistently cause positive reactions in indirect antiglobulin tests (IATs), antibody detection (screening) tests, antibody identification panels, and antihuman globulin (AHG) crossmatches. Agglutination due to anti-CD38 may occur in all media (eg, saline, low ionic strength saline, polyethylene glycol),

and with all IAT methods (eg, gel, tube, solid phase). Agglutination reactions caused by anti-CD38 are usually weak (1+), but stronger reactions (up to 4+) may be seen in solid-phase testing. However, anti-CD38 does NOT interfere with ABO/RhD typing or with immediate-spin crossmatches.

Other notes on anti-CD38 serologic interference:

- Adsorptions using either untreated or ZZAP-treated cells fail to eliminate the interference.
- Anti-CD38 variably interferes with direct antiglobulin tests (DATs) and antibody identification panel autocontrols.
- Some rare Lu(a-b-) cells are not reactive in the presence of anti-CD38, potentially giving the false impression that the patient has a Lutheran-related antibody.^{4,5}
- Positive IATs can be observed for up to six months after anti-CD38 is discontinued.^{1,3}
- Anti-CD38 may cause a small decrease in hemoglobin *in vivo* (~1 g/dL), but severe hemolysis has not been observed among treated patients.^{3,6}

Anti-CD38 interference can cause delays in issuing RBCs

If the transfusion service is unaware that a patient has received anti-CD38, the following scenario may occur when the patient's sample is tested:

1. ABO/RhD typing: no issues.
2. Antibody detection (screening) test: all cells positive.
3. Antibody identification panel: all cells positive (autocontrol may be negative).
4. DAT: positive or negative.
5. AHG crossmatches: positive with all RBC units tested.
6. Adsorptions: panreactivity cannot be eliminated.

This leads to delays in issuing RBCs to the patient. In some cases, the anti-CD38 interference could mask the presence of a clinically significant alloantibody.

Recommendations

To avoid problems with transfusion, hospitals should set up procedures to inform the transfusion service whenever any patient is scheduled to begin taking anti-CD38.

BEFORE a patient begins taking anti-CD38:

- A baseline type and screen should be performed.
- In addition, a baseline phenotype or genotype is recommended.

AFTER a patient begins taking anti-CD38:

- ABO/RhD typing can be performed normally.
- For antibody detection (screening) and identification, dithiothreitol (DTT)-treated cells can be used to eliminate the interference.^{2,7}
 - Because DTT treatment destroys Kell antigens, K-negative units should be provided unless the patient is known to be K-positive.
 - Antibodies against other DTT-sensitive blood group antigens (anti-k, anti-Yt^a, anti-Do^a/Do^b, etc) will not be detectable when the antibody screen with DTT-

treated cells is performed; such antibodies are encountered infrequently, however.

Crossmatch

- For patients with a negative antibody screen using DTT-treated cells, an electronic or immediate-spin crossmatch with ABO/RhD-compatible, K-matched units may be performed.
- For patients with known alloantibodies, phenotypically or genotypically matched RBC units may be provided.^{6,8}
 - As some typing antisera require the use of AHG, phenotyping should be performed before the patient receives anti-CD38.
 - Genotyping can be performed either before or after the patient receives anti-CD38.
 - AHG crossmatches with phenotypically or genotypically matched units will still be incompatible.
 - Some clinically significant antibodies may be missed with the use of uncrossmatched phenotypically or genotypically matched units, although this will occur infrequently.
- Alternatively, an AHG crossmatch may be performed using DTT-treated donor cells.
- If an emergency transfusion is required, uncrossmatched ABO/RhD-compatible RBCs may be given per local blood bank practices.

Future/alternative approaches to mitigating the anti-CD38 interference

It is possible to neutralize anti-CD38 in plasma and eliminate the interference using either recombinant soluble human CD38 or daratumumab idiotype antibody.¹³ Neither reagent is widely available at this time, and additional validation would be needed. In principle, soluble CD38 could be used to neutralize any anti-CD38, while different idiotype antibodies would be needed to neutralize different CD38 therapeutic antibodies. Finally, antigen-typed cord cells have been used for the antibody screen as an alternative to DTT-treated cells.⁹

References

1. Darzalex package insert. Horsham, PA: Janssen Biotech, 2015. [Available at: <http://www.darzalex.com/shared/product/darzalex/darzalex-prescribing-information.pdf> (accessed January 7, 2016).]
3. Oostendorp M, Lammerts van Bueren JJ, Doshi P, et al. When blood transfusion medicine becomes complicated due to interference by monoclonal antibody therapy. *Transfusion* 2015;55(6pt2):1555-62.
